4. SUBJECT ELIGIBILITY CRITERIA

The following eligibility criteria are designed to select subjects for whom participation in the study is considered appropriate. All relevant medical and nonmedical conditions should be taken into consideration when deciding whether a particular subject is suitable for this protocol.

This study will enroll children and adolescents with Bipolar I Disorder, who have participated in double blind Study A1281198. In order to be enrolled in this open label extension trial, subjects must have met the enrollment criteria for Study A1281198, and must meet the following inclusion and exclusion criteria at the A1281201 extension study Baseline visit (last visit in the double blind study). Any questions regarding eligibility must be discussed with a Pfizer clinician prior to the subject's participation in the study.

Subject eligibility should be reviewed and documented by an appropriate member of the investigator's study team before subjects are included in the study. A statement that the subject was eligible to enter the clinical trial should be completed by the investigator and included in the subject's source documentation.

4.1. Inclusion Criteria

Subjects must meet all of the following inclusion criteria to be eligible for enrollment into the study:

1. Evidence of personally signed and dated informed consent document by the legal representative and an assent document by the subject indicating that the subject and a legal representative have been informed of all pertinent aspects of the study.
2. Subjects and their legal guardians who are willing and able to comply with scheduled visits, treatment plan, laboratory tests, and other study procedures.
3. The subjects must have received investigational product in Study A1281198 and completed at least 3 weeks of double blind treatment before entering this open label extension. However, subjects who have insufficient treatment response and have reached their maximum tolerated dose may enroll in the open label extension as early as 1 week after the end of their titration.
4. In the investigator's opinion, the subject must be likely to benefit from antipsychotic therapy and must have been free from any clinically significant safety concerns during the preceding double blind study (ie, in the opinion of the investigator, the benefits that the subject is likely to derive from continued participation must outweigh the risks).
5. All fertile male subjects and female subjects of childbearing potential who are sexually active and/or their legal guardians, as appropriate, must agree that a highly effective method of contraception be used as outlined in this protocol and for the duration of the study and for 28 days after the last dose of investigational product.

4.2. Exclusion Criteria

Subjects with any of the following characteristics/conditions will not be included in the study:

1. Any subjects from the preceding double blind trial who experienced a serious adverse event which required study medication to be discontinued and the subject to be withdrawn from the study. Subjects who experienced cardiac arrhythmias, conduction abnormalities, or QTc prolongation (confirmed and persistent Fridericia's correction (QTcF) >480 msec or increase from baseline QTcF >60 msec) during the preceding study.
2. Subjects requiring any medications not allowed by the Concomitant Medication [Table 12](#) (see “[Concomitant Treatment\(s\)](#)”).
3. Subjects who require treatment with drugs that are known to consistently prolong the QT interval (see Concomitant Medication [Table 12](#)).
4. Subjects who are judged by the investigator as being at imminent risk of suicide.
5. Subjects living in the same home as another study participant or having the same caregiver during the same enrollment period (Such subjects can be enrolled in the study at different times but may not be in the study at the same time).
6. Subjects should be excluded or a risk assessment should be done to verify that it is safe for the subject to participate in the trial if the subject's responses on the C-SSRS or other information based on the investigator's judgment indicate:
 - Suicide ideation associated with actual intent and a method or plan such that a positive response ('Yes') is made on items 4 or 5 of the suicidal ideation subscale of the C-SSRS; or
 - Any suicide behaviors such that a determination of 'yes' is made to any of the suicide behavior items of the C-SSRS.
7. Pregnant female subjects, breastfeeding female subjects.
8. Participation in other studies other than the preceding Study.
9. Other acute or chronic medical or psychiatric condition including recent (within the past year) or active suicidal ideation or behavior or laboratory abnormality that may increase the risk associated with study participation or investigational product administration or may interfere with the interpretation of study results and, in the judgment of the investigator, would make the subject inappropriate for entry into this study.

4.3. Randomization Criteria

Not applicable.

4.4. Lifestyle Requirements

N/A.

4.4.1. Contraception

All fertile male subjects and female subjects who are of childbearing potential, as applicable to the study who are, in the opinion of the investigator, sexually active and at risk for pregnancy with their partner(s), must agree to use a highly effective method of contraception consistently and correctly for the duration of the active treatment period and for at least 28 days after the last dose of investigational product. The investigator or his or her designee will confirm that the subject has selected an appropriate method of contraception from the list of permitted contraception methods (see below). At time points indicated in the [Schedule of Activities](#), the investigator or designee will instruct the subject of the need to use highly effective contraception consistently and correctly and document the conversation, and the subject's affirmation, in the subject's chart. In addition, the investigator or designee will instruct the subject to call immediately if the selected contraception method is discontinued or if pregnancy is known or suspected in the subject or partner.

Highly effective methods of contraception are those that, alone or in combination, result in a failure rate of less than 1% per year when used consistently and correctly (ie, perfect use) and include the following:

1. Established use of hormonal methods of contraception associated with inhibition of ovulation (eg, oral, inserted, injected, implanted, transdermal), provided the subject plans to remain on the same treatment throughout the entire study and has been using that hormonal contraceptive for an adequate period of time to ensure effectiveness.
2. Correctly placed copper-containing intrauterine device (IUD).
3. Male condom or female condom used WITH a separate spermicide product (ie, foam, gel, film, cream, or suppository). For countries where spermicide is not available or condom plus spermicide is not accepted as highly effective contraception, this option is not appropriate.

NOTE: Sexual abstinence, defined as completely and persistently refraining from all heterosexual intercourse (including during the entire period of risk associated with the study treatments) may obviate the need for contraception ONLY if this is the preferred and usual lifestyle of the subject.

All sexually active male subjects must agree to prevent potential transfer to and exposure of partner(s) to drug through ejaculate by using a condom consistently and correctly, beginning with the first dose of investigational product and continuing for at least 28 days after the last dose of investigational product.

4.5. Sponsor's Qualified Medical Personnel

To facilitate access to appropriately qualified medical personnel on study-related medical questions or problems, subjects are provided with a contact card. The contact card contains, at a minimum, protocol and investigational product identifiers, subject study numbers, contact information for the investigator site, and contact details for a contact center in the event that the investigator site staff cannot be reached to provide advice on a medical question or problem originating from another healthcare professional not involved in the subject's participation in the study. The contact number can also be used by investigator staff if they are seeking advice on medical questions or problems; however, it should be used only in the event that the established communication pathways between the investigator site and the study team are not available. It is therefore intended to augment, but not replace, the established communication pathways between the investigator site and the study team for advice on medical questions or problems that may arise during the study. The contact number is not intended for use by the subject directly, and if a subject calls that number, he or she will be directed back to the investigator site.

5. STUDY TREATMENTS

For the purposes of this study, and per International Conference on Harmonisation (ICH) guidelines, investigational product is defined as a pharmaceutical form of an active ingredient or placebo being tested or used as a reference/comparator in a clinical trial, including a product with a marketing authorization when used or assembled (formulated or packaged) in a way different from the approved form, or when used for an unapproved indication, or when used to gain further information about an approved use (ICH E6 1.33).

For this study, the investigational product is Ziprasidone Hydrochloride.

5.1. Allocation to Treatment

Throughout most of this study, ziprasidone will be administered as open label (OL) investigational product to all subjects.

However, the dose transition from the double-blind study drug administered in Study A1281198 to the open-label dosing in the extension trial A1281201 will be conducted under double-blind conditions.

The double-blind dose transition phase of Study A1281201 will comprise Weeks 1 and 2 for subjects ≥ 45 kg and Week 1 for subjects < 45 kg. The double-blind (DB) medication for this transition period will be assigned according to the subject's randomization number in the preceding study so that the investigator remains blinded during this period.

At the baseline visit of the A1281201 study, subjects will transition onto active medication if previously assigned to the placebo group or continue on active study drug. Over the course of the double-blind dose transition period, subjects < 45 kg will be transitioned to a total daily dose of 60 mg a day by Day 7 of Week 1 and subjects ≥ 45 kg will be transitioned to a total daily dose of 120 mg a day by Day 10 of Week 2. (Subjects on 160 mg, 140 mg, 100 mg, and 80 mg active at the end of Study A1281198 will all be transitioned to 120 mg a day at the

end of the two-week transition period. Subjects on 120 mg active at the end of Study A1281198 will remain on 120 mg a day through the dose transition period).

Any subject who cannot tolerate the transition study medication during Week 1 should be discontinued from the study.

All medication will remain blinded until the end of the transition period. Diagrams of the transition dosing cards for subjects who were on placebo or ziprasidone in Study A1281198 are provided in [Table 1](#), [Table 2](#), [Table 3](#) and [Table 4](#).

At the end of the double-blind transition period, all subjects will start to receive open label ziprasidone. Diagrams of the double-blind dose transition study drug blister cards are provided in [Table 1](#), [Table 2](#), [Table 3](#) and [Table 4](#).

Allocation of subjects to treatment groups will precede through the use of an interactive response technology (IRT) system (interactive Web-based response [IWR]). The site personnel (study coordinator or specified designee) will be required to enter or select information including but not limited to the user's identification (ID) and password, the protocol number, and the subject number. The site personnel will then be provided with a treatment assignment, randomization number, and dispensable unit (DU) or container number when investigational product is being supplied via the IRT system. The IRT system will provide a confirmation report containing the subject number, randomization number, and DU or container number assigned. The confirmation report must be signed by two appropriate staff members and stored in the site's file.

The study-specific IRT reference manual will provide the contact information and further details on the use of the IRT system.

5.2. Breaking the Blind

As Applicable.

5.3. Subject Compliance

The investigator must maintain a complete and current dispensing and inventory record that has been supplied by the sponsor.

Study personnel at the site should monitor compliance at each study visit according to the [Schedule of Activities](#) by comparing the returned study drug contained within the blister cards keeping in mind the prescribed dose with the dose information reported by the subject on the diary card. Discrepancies between returned capsule counts from the blister cards and subject reported dose information on the subject diary cards should be reconciled with the subject and/or legal guardian during the office visit. Compliance and any unresolved discrepancies will be documented in the source documents and on the Investigational Product Accountability Log. The study drug CRF (case report form) page should reflect the reconciled dose information provided by the subject and/or legal guardian.

In addition, photocopies should be made of both sides of the returned blister cards. The photocopies should be dated and signed and kept as part of the source documentation.

The subject diary cards and the photocopies of the blister cards will serve as the source documentation of what medication was taken as the actual blister cards will eventually be destroyed according to drug accountability procedures (see [Section 5.8](#)). Information from the subject diary card will be included on the study drug CRF page.

A subject will be considered non-compliant with respect to dosing if the subject misses more than 20% of their scheduled doses over the entire study. Such a condition will be considered a protocol violation and the subject will be excluded from the per protocol (PP) analysis set.

5.4. Investigational Product Supplies

5.4.1. Dosage Form and Packaging

All investigational products will be provided by Pfizer and will include oral ziprasidone capsules of 20, 40, 60, and 80 mg strength. Matching placebo capsules may also be supplied for the initial 1-14 day dose transition period. All medication will be packaged in childproof blister cards with columns for AM and for PM capsules.

Two different types/designs of child resistant blister cards will be provided over the course of the study: a transition card design and a fixed dose card design. Each transition card will contain medication for 7 days plus 3 additional days. Each fixed dose card will contain 7 days of medication per card plus 1 additional day for use in the open label phase. During the transition phase, all blister cards will have 1 to 2 capsules available for the AM and 1 to 2 capsules for the PM administration. During the open label phase (Weeks 2/3-26), the blister cards will have only 1 capsule available for the AM and 1 capsule available for the PM dose of active medication. Each of the AM or PM columns will contain a 20 mg, 40 mg, 60 mg or 80 mg ziprasidone capsules (or matching placebo) during the transition and only active ziprasidone capsules during open-label treatment. The target dose ranges for subjects <45 kg is 60 to 80 mg/day and for subjects ≥45 kg, 120 to 160 mg/day, which are identical to the target dose ranges used in study A1281198.

For more information please refer to the Investigational Product manual for all items related to IP.

Dose Transition Card Container Types	
Double-Blind Dose Transition Card	
Active Ziprasidone or Placebo (separate cards for Day 1/Baseline and Week 2/Visit 2)	≥45 kg body weight
Active Ziprasidone or Placebo (Day 1/Baseline)	<45 kg body weight

In order to accommodate the flexible dosing permitted by the protocol following the dose transition period, 7 types of open label fixed dosing cards, each with a different total daily dose of study drug as described in below tables:

Fixed Dose OL Card Container Types		
Total Daily Dose	AM Dose	PM Dose
40 mg	20 mg	20 mg
60 mg	20 mg	40 mg
80 mg	40 mg	40 mg
100 mg	40 mg	60 mg
120 mg	60 mg	60 mg
140 mg	60 mg	80 mg
160 mg	80 mg	80 mg

5.4.2. Preparation and Dispensing

On Day 1 (Baseline Visit), one transition card will be dispensed based on the subject's weight (≥ 45 kg or < 45 kg) and previously assigned treatment in Study A1281198 for the first week of dosing. Only subjects ≥ 45 kg will receive a transition card at Week 2 if needed. After Week 1, subjects from the < 45 kg group will be provided a fixed dose card for the second week of the dose transition phase. Medication dose- and weight-based tables illustrate the dosing sequence subjects will be assigned during the transition periods by weight and current assigned dose in A1281198 ([Table 1](#), [Table 2](#), [Table 3](#) and [Table 4](#)).

Patients < 45 kg will be assigned a 60 mg active/placebo titration card at Day 1 of A1281201. Patients ≥ 45 kg will be assigned one of three dose levels: Patients on the 80 mg or 100 mg dose level in A1281198 will be given a 100 mg active/placebo titration card Day 1 of A1281201, Patients on the 120 mg dose level in A1281198 will be given a 120 mg active/placebo titration card Day 1 of A1281201, and Patients on the 140 mg or 160 mg dose level in A1281198 will be given a 140 mg active/placebo titration card Day 1 of A1281201.

After the baseline visit, the investigator or designed staff must be in contact with the subject and his/her legal guardian(s) on at least one occasion between the baseline visit and the Week 1 visit and between the Week 1 visit and the Week 2 visit, either by telephone or in person, to ensure that the subject is taking the proper capsules at the proper time and to monitor the tolerability and efficacy of the titration plan.

After the Week 6 visit, the investigator or designated staff must be in contact with the subject and his/her parent(s) and/or guardian(s) in between study visits by telephone to ensure that the subject is taking the proper capsules at the proper time and to monitor the tolerability and efficacy of the study medication.

Table 1. Double-Blind Dose Transition Blister Cards for ≥ 45 kg Subjects on 160 mg/day or 140 mg/day of Active Ziprasidone or Placebo at End of Study A1281198, Weeks 1 and 2

140 mg Week 1 Active Titration Card			
Day	AM Dose (mg)	PM Dose (mg)	Total Daily Dose (mg)
1		80	140/160*
2	60	80	140
3	60	80	140
4	60	80	140
5	60	80	140
6	60	80	140
7	60	80	140
8	60	80	140

140 mg Week 1 Placebo Titration Card			
Day	AM Dose (mg)	PM Dose (mg)	Total Daily Dose (mg)
1		20	20
2	20	20	40
3	20	20	40
4	20	40	60
5	20	40	60
6	40	40	80
7	40	40	80
8	40	40	80

* Subjects on a dose of 160 mg at the end of the A1281198 study will remain at that dose for 1 additional day during the transition period due to the Day 1 card PM dose design. Starting on Day 2 of the transition period these subjects will receive a total daily dose of 140 mg/day.

120 mg Week 2 Active Titration Card			
Day	AM Dose (mg)	PM Dose (mg)	Total Daily Dose (mg)
1		60	120
2	60	60	120
3	60	60	120
4	60	60	120
5	60	60	120
6	60	60	120
7	60	60	120
8	60	60	120

120 mg Week 2 Placebo Titration Card			
Day	AM Dose (mg)	PM Dose (mg)	Total Daily Dose (mg)
1	40	60	100
2	40	60	100
3	60	60	120
4	60	60	120
5	60	60	120
6	60	60	120
7	60	60	120
8	60	60	120

Table 2. Double-Blind Dose Transition Blister Cards for ≥ 45 kg Subjects on 120 mg/day of Active Ziprasidone or Placebo at End of Study A1281198, Weeks 1 and 2

120 mg Week 1 Active Titration Card			
Day	AM Dose (mg)	PM Dose (mg)	Total Daily Dose (mg)
1		60	120
2	60	60	120
3	60	60	120
4	60	60	120
5	60	60	120
6	60	60	120
7	60	60	120
8	60	60	120

120 mg Week 1 Placebo Titration Card			
Day	AM Dose (mg)	PM Dose (mg)	Total Daily Dose (mg)
1		20	20
2	20	20	40
3	20	20	40
4	20	40	60
5	20	40	60
6	40	40	80
7	40	40	80
8	40	40	80

120 mg Week 2 Active Titration Card			
Day	AM Dose (mg)	PM Dose (mg)	Total Daily Dose (mg)
1	60	60	120
2	60	60	120
3	60	60	120
4	60	60	120
5	60	60	120
6	60	60	120
7	60	60	120
8	60	60	120

120 mg Week 2 Placebo Titration Card			
Day	AM Dose (mg)	PM Dose (mg)	Total Daily Dose (mg)
1	40	60	100
2	40	60	100
3	60	60	120
4	60	60	120
5	60	60	120
6	60	60	120
7	60	60	120
8	60	60	120

Table 3. Double-Blind Dose Transition Blister Cards for ≥ 45 kg Subjects on 80 mg/day or 100 mg of Active Ziprasidone or Placebo at End of Study A1281198, Weeks 1 and 2

100 mg Week 1 Active Titration Card			
Day	AM Dose (mg)	PM Dose (mg)	Total Daily Dose (mg)
1		60	100*
2	40	60	100
3	40	60	100
4	40	60	100
5	40	60	100
6	40	60	100
7	40	60	100
8	40	60	100

100 mg Week 1 Placebo Titration Card			
Day	AM Dose (mg)	PM Dose (mg)	Total Daily Dose (mg)
1		20	20
2	20	20	40
3	20	20	40
4	20	40	60
5	20	40	60
6	40	40	80
7	40	40	80
8	40	40	80

* Subjects who were assigned 80 mg at the end of Study A1281198 will have a 20 mg increase in dose starting on Day 1 of the double blind transition period due to the design of the transition dose card.

120 mg Week 2 Active Titration Card			
Day	AM Dose (mg)	PM Dose (mg)	Total Daily Dose (mg)
1	60	60	120
2	60	60	120
3	60	60	120
4	60	60	120
5	60	60	120
6	60	60	120
7	60	60	120
8	60	60	120

120 mg Week 2 Placebo Titration Card			
Day	AM Dose (mg)	PM Dose (mg)	Total Daily Dose (mg)
1	40	60	100
2	40	60	100
3	60	60	120
4	60	60	120
5	60	60	120
6	60	60	120
7	60	60	120
8	60	60	120

Table 4. Double Blind Dose Transition Blister Cards for <45 kg Subjects on 40 mg/day, 60 mg/day, or 80 mg of Active Ziprasidone or Placebo at End of Study A1281198, Week 1

60 mg Week 1 Active Titration Card				60 mg Week 1 Placebo Titration Card			
Day	AM Dose (mg)	PM Dose (mg)	Total Daily Dose (mg)	Day	AM Dose (mg)	PM Dose (mg)	Total Daily Dose (mg)
1		40	60/80*	1		20	20
2	20	40	60	2	20	20	40
3	20	40	60	3	20	20	40
4	20	40	60	4	20	20	40
5	20	40	60	5	20	40	60
6	20	40	60	6	20	40	60
7	20	40	60	7	20	40	60
8	20	40	60	8	20	40	60

* Subjects who were assigned 40 mg at the end of Study A1281198 will have a 20 mg increase in dose starting on Day 1 of the double blind transition period due to the design of the transition dose card. Subjects who were assigned 80 mg at the end of Study A1281198 will receive 80 mg on Day 1 of the dose transition week but from Day 2 onwards will receive a total daily dose of 60 mg/day.

Subjects weighing <45 kg should be issued an open label, fixed dosing card with the desired total daily dose for the second week of the dose transition phase(ie, either 40 mg/day, 60 mg/day, or 80 mg/day; see Table 5, [Table 6](#), or [Table 7](#)).

The investigator will decide which fixed dose blister card to provide to the subject for the following week, based on clinical judgment.

Table 5. 40 mg Fixed Dose Regimen

Day	AM Dose (mg)	PM Dose (mg)	Total Daily Dose (mg)
1	20	20	40
2	20	20	40
3	20	20	40
4	20	20	40
5	20	20	40
6	20	20	40
7	20	20	40
8	20	20	40

Table 6. 60 mg Fixed Dose Regimen

Day	AM Dose (mg)	PM Dose (mg)	Total Daily Dose (mg)
1	20	40	60
2	20	40	60
3	20	40	60
4	20	40	60
5	20	40	60
6	20	40	60
7	20	40	60
8	20	40	60

Table 7. 80 mg Fixed Dose Regimen

Day	AM Dose (mg)	PM Dose (mg)	Total Daily Dose (mg)
1	40	40	80
2	40	40	80
3	40	40	80
4	40	40	80
5	40	40	80
6	40	40	80
7	40	40	80
8	40	40	80

Subjects weighing ≥ 45 kg should be issued an open label fixed dosing card with the desired total daily dose at the start of the third week (Day 15) of the extension study (ie, either 80 mg/day, 100 mg/day, 120 mg/day, 140 mg/day or 160 mg/day total daily dose; see Table 8-[Table 11](#)).

Table 8. 100 mg Fixed Dose Regimen

Day	AM Dose (mg)	PM Dose (mg)	Total Daily Dose (mg)
1	40	60	100
2	40	60	100
3	40	60	100
4	40	60	100
5	40	60	100
6	40	60	100
7	40	60	100
8	40	60	100

Table 9. 120 mg Fixed Dose Regimen

Day	AM Dose (mg)	PM Dose (mg)	Total Daily Dose (mg)
1	60	60	120
2	60	60	120
3	60	60	120
4	60	60	120
5	60	60	120
6	60	60	120
7	60	60	120
8	60	60	120

As a reminder subjects weighing ≥ 45 kg could be provided the 140 or 160 mg/day fixed dose card (see Table 10 and Table 11) only if they have tolerated 120 mg/day; in addition, the 140 and 160 mg/day fixed dose card should not be issued before Day 15 of the study.

Table 10. 140 mg Fixed Dose Regimen

Day	AM Dose (mg)	PM Dose (mg)	Total Daily Dose (mg)
1	60	80	140
2	60	80	140
3	60	80	140
4	60	80	140
5	60	80	140
6	60	80	140
7	60	80	140
8	60	80	140

Table 11. 160 mg Fixed Dose Regimen

Day	AM Dose (mg)	PM Dose (mg)	Total Daily Dose (mg)
1	80	80	160
2	80	80	160
3	80	80	160
4	80	80	160
5	80	80	160
6	80	80	160
7	80	80	160
8	80	80	160

Only site personnel according to their role as determined on the site delegation log may dispense investigational product cards. Subjects will be instructed to take medication with food and to take one capsule in the AM and one capsule in the PM from each assigned blister card during the open label phase.

The investigational product will be dispensed using an IRT drug management system at each visit from baseline to Week 22. A qualified staff member will dispense the investigational product, a unique container numbers on the blister cards provided, in quantities appropriate for the study visit schedule. The subject/caregiver should be instructed to maintain the product in the blister cards, as provided throughout the course of dosing and return the blister cards, to the site at the next study visit.

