ET = early termination; BMI = Body Mass Index; ECG = Electrocardiogram; T4 = Thyroxin 4; TSH= Thyroid-Stimulating Hormone; HbA1c = glycated hemoglobin; YMRS = Young Mania Rating Scale; CGI-S = Clinical Global Impressions of Severity; CGAS =Children's Global Assessment Scale; CDRS-R = Child Depression Rating Scale - Revised; SARS = Simpson Angus Rating Scale; BAS = Barnes Akathisia Rating Scale; AIMS = Abnormal Involuntary Movement Scale; C-SSRS = Columbia Suicide Severity Rating Scale.

* All ECGs will be administered at least 3 hours after food intake.

** Subjects should remain fasting for at least 8 hours prior to the baseline visit, Week 6, Week 18, and Week 26..

- a. Baseline Visit is the last visit of the preceding double-blind trial, Study A1281198. In the case of early termination, all procedures specified for Week 26/ET are to be completed.
- b. Every effort should be made to bring the subject back to the office on the designated study days; however, monthly office visits will have a ± 3 day visit window to allow for slight variations in subject schedules. When scheduling subsequent visits, the overall treatment period in the protocol should be maintained.
- c. Subjects who turn 18 years old during the study need to give a written consent.
- d. Only if the subject had clinically significant abnormal findings from a previous visit that require follow-up.
- e. ECGs showing a QTcF of >480 msec or a suspected increase from baseline of 60 msec or greater must be repeated within the same visit. If the QTcF value persists at >480 msec and/or the change from baseline persists at >60 msec, the study drug must be discontinued immediately and a pediatric cardiologist or an adult cardiologist experienced in the interpretation of pediatric ECGs should be contacted to discuss the ECG result.
- f. The subject should be in the sitting position for approximately 5 minutes and in the standing position for approximately 2 minutes before the measurements are obtained.
- g. Following the baseline visit, unscheduled urine drug screens can be performed at additional visits at the investigator's discretion.

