5.8. Investigational Product Accountability

The investigator site must maintain adequate records documenting the receipt, use, loss, or other disposition of the investigational product supplies. All investigational products will be accounted for using a drug accountability form/record. All blister cards of study drug must be returned to the investigator by the subject at every visit and at the end of the trial.

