6.2. Study Visits During Open-label Treatment

Subjects will attend study visits at Weeks 1, 2, 4, 6, 10, 14, 18, 22, and 26 (or early termination). There will also be a brief follow-up (off treatment) visit at Week 27. The following will be assessed or administered at EVERY on-treatment visit:

- Adverse events;
- Review of concomitant medications;
- Blood pressure and pulse;
- Drug accountability (Document drug returned and record any dosage changes, except Day 1);
- Dispense study drug (except Week 26 or early termination);
- Double-blind transition card provided only for ≥ 45 kg weight group subjects (Week 1);
- CGI-S;
- C-SSRS;

- CDRS-R;
- Movement disorder scales (SARS, BAS, AIMS);
- A urine pregnancy test will be obtained on all female subjects at all study visits. A positive urine pregnancy test should be confirmed with a serum pregnancy test.
- Verification of contraception.

At week 4 in addition to the above the following will be assessed or administered:

- Electrocardiogram.

At Weeks 1, 2, 6, 14, 22 and 26 (or early termination), in addition to the above, the following will be assessed or administered:

- YMRS;
- Electrocardiogram.

At Weeks 6 and 26 (or early termination), in addition to the above, the following will be assessed or administered:

- Clinical laboratory tests (chemistry, hematology, urinalysis) and urine drug screen;
- Body weight, height, BMI, BMI z score, and waist circumference;
- Hormones (free T4 & TSH (thyroid stimulating hormone), Prolactin).

At Weeks 6, 18, and 26 (or early termination), in addition to the above, the following will be assessed or administered:

- Fasting glucose, lipid profile, insulin and glycated hemoglobin (HbA1c).

The following will be done only at Week 26 (or early termination):

- Physical exam;
- CGAS.

A urine pregnancy test will be obtained on all female subjects at all study visits. A positive urine pregnancy test should be confirmed with a serum pregnancy test.

Following the baseline visit, unscheduled urine drug screens can be performed at additional visits at the investigator's discretion.

Since no investigational product will be available after the Week 26 visit, the physician may initiate appropriate treatment with commercially available medications.

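### Table 1, 120 mg Week 2 active card: the Day 1 row has no morning dose and gives 60 mg, but its printed total is 120 mg

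*Protocol*

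**What the plan says.** Protocol 5.4.2, Tables 1 to 3, lists morning, evening and total daily doses for the double-blind transition cards of subjects weighing 45 kg or more. Each table pairs an active card, for subjects who were on ziprasidone, with a placebo card, for former placebo subjects who are being titrated up on ziprasidone.

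The "120 mg Week 2 Active Titration Card" appears in all three tables. In Tables 2 and 3 its Day 1 row reads 60, 60, total 120. In Table 1 the Day 1 row reads blank, 60, total 120, and Days 2 to 8 read 60, 60, 120. The "120 mg Week 2 Placebo Titration Card" reads 40, 60, total 100 on Day 1 in all three tables.

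Blank Day 1 mornings are deliberate on the Week 1 cards: the first dose from the card is the evening dose, and the morning dose belongs to the preceding study. The Table 1 footnote explains this for subjects on 160 mg and continues: "Starting on Day 2 of the transition period these subjects will receive a total daily dose of 140 mg/day". No similar note covers a Week 2 card.

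Protocol 5.4.1 says that transition cards carry one or two capsules for the morning and for the evening, and makes no exception for any card. It also refers to the Investigational Product manual for further detail.

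**The concern.** One row of an operative dosing table does not add up, and the row that fails is the only one of the six Week 2 Day 1 rows without a morning dose. If the card were packaged and used as printed from the morning, a subject previously on 140 or 160 mg of active drug would go from 140 mg to 60 mg for one day and then to 120 mg. The intended step is from 140 mg directly to 120 mg.

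The row also differs from its placebo partner, which has a 40 mg morning dose on Day 1. Protocol 5.1 keeps medication blinded until the transition ends. A pocket that is empty on one card of the pair and filled on the other could show which treatment the subject had received.

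**Working it through.** **Inputs.** All are in mg and come from Protocol 5.4.2, Tables 1 to 3: the morning dose in the Day 8 row of each Week 1 card, and the Day 1 morning dose, evening dose and printed total of each Week 2 card.

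**Formulas.**
- Morning start: Week 2 Day 1 morning + Week 2 Day 1 evening, with a blank counted as 0.
- Evening start: Week 1 Day 8 morning + Week 2 Day 1 evening.
- Corrected: morning start with the blank cell set to 60.

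| Week 2 card | Week 1 Day 8 AM | Day 1 AM | Day 1 PM | Printed total | Morning start | Evening start | Corrected |
|---|---|---|---|---|---|---|---|
| Table 1 active | 60 | blank | 60 | 120 | **60** | 120 | 120 |
| Table 1 placebo | 40 | 40 | 60 | 100 | 100 | 100 | 100 |
| Table 2 active | 60 | 60 | 60 | 120 | 120 | 120 | 120 |
| Table 2 placebo | 40 | 40 | 60 | 100 | 100 | 100 | 100 |
| Table 3 active | 40 | 60 | 60 | 120 | 120 | **100** | 120 |
| Table 3 placebo | 40 | 40 | 60 | 100 | 100 | 100 | 100 |
| Totals reproduced | | | | | 5 of 6 | 5 of 6 | 6 of 6 |

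The printed 120 mg for Table 1 active is not reproduced from its own row. It is reproduced if 60 mg is carried over from the Week 1 card, but the same rule then gives 40 + 60 = 100 on Table 3 active, against 120 printed. With an evening start and no morning dose at all, every card gives 60 mg and none of the six totals is reproduced.

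A rule with an evening start for Table 1 active and a morning start for the other cards would also match all six totals. The protocol states no such rule, and it would treat the two cards of the Table 1 pair differently.

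**Likely origin.** The eight rows of the Table 1 Week 2 active card are identical to those of the Table 2 Week 1 active card, where the blank first morning is intended. A copying slip is the simplest explanation.

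**Size of the worst case** (card built as printed, started in the morning, not corrected):
- Handover day: 60 mg instead of 120 mg, which is 60/120 = 50%.
- Seven days: 60 + 6 × 120 = 780 mg against 7 × 120 = 840 mg; (780 - 840)/840 = -7.1%.

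**Best case** (morning dose already taken from the Week 1 card): 60 + 60 = 120 mg, so there is no shortfall.

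**The case against.** The strongest reply is that this is a single-cell slip whose intended value is obvious. The card's name, its printed total and its seven other rows all point to 60 mg, and so does the account of card contents in 5.4.1. That stands, and it is why the point is minor. It does not make the printed row correct. The 5.4.1 sentence is also not decisive for a single pocket, because the Week 1 cards have intended blanks on Day 1.

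A digit lost when the PDF was converted to text cannot be excluded. It is less likely, because the empty cell has the same form as the deliberate Week 1 blanks, but the source table should be checked first.

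A reader might infer three stronger things, and the documents support none of them.

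- **Subjects will be underdosed.** A shortfall needs a card built without the capsule, a morning start from that card, and no correction by anyone. The protocol requires site contact with the family between the Week 1 and Week 2 visits (5.4.2), reconciliation of diary and returned cards (5.3), and a missed-dose rule (5.5).
- **The blind is broken.** The tables list milligrams, not capsules, and 5.4.1 allows matching placebo capsules in transition cards. A morning without ziprasidone need not look empty. A visible difference is possible but not shown.
- **The protocol leaves the change of cards undefined.** Section 6.2 places the second card at the Week 1 visit, and under 5.8 "All blister cards of study drug must be returned to the investigator by the subject at every visit". After that visit the subject holds the new card, so the next dose comes from it. The protocol does not name the exact dose at which to switch, but it refers to the Investigational Product manual, which is not available here. Likewise, the difference between eight printed rows and the ten days of medication in 5.4.1 does not show a dosing error. The target date for 120 mg needs no rewording, because 5.5 already allows Days 7 to 14 in general.

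**Conclusion.** The row is wrong as written, and the point is minor. Day 1 of the Table 1 Week 2 active card gives 60 mg against a printed 120 mg. No single start time reproduces all six Week 2 Day 1 totals until the blank cell is filled.

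The shortfall lies between 0 and 60 mg on one day, at worst 7.1% of one week's dose. It applies only to subjects previously on active 140 or 160 mg. The size of that group is not given; it is some part of the approximately 55 expected entrants (Protocol 9.1). The possible visible difference between paired cards depends on how they were packaged, which the documents do not show.

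No planned analysis is affected. The SAP uses one safety set of everyone who took at least one dose in the extension (4.1), and its summaries are descriptive (5.2).

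The conclusion assumes that the blank is also in the source table and that one start time was meant for all six cards.

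**What to change.** Confirm the cell against the source table and enter 60 mg as the Day 1 morning dose of the Table 1 Week 2 active card. All six Day 1 totals then hold for a morning start. Check that the packaged active and placebo Week 2 cards have the same filled pockets.

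The cost is one table cell and one packaging check. No visit, procedure or analysis changes, and no new dispensing text is needed.
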